11.3.1.8 Modification 8: Assessments for patients who continue on open-label darolutamide treatment

To clarify the transition to open-label treatment phase, a start of open-label treatment visit and subsequent visit schedule were added for those patients who choose to receive open-label darolutamide after unblinding. The schedule of procedures (e.g. QoL, biomarker sampling, drug dispensing and accountability) was updated accordingly.

Four-monthly imaging will be continued to ensure to follow-up patients in the darolutamide open-label arm for MFS. Local reading is considered to be adequate during the open-label treatment phase, no central confirmation is required.

In addition, it was added that ECG and PK sampling are not required during the open-label darolutamide treatment.

Protocol sections affected: Synopsis, 1.6.1 Rationale of the study design, 4.7.2.1 Confirmed metastasis, 5.8 Treatment compliance and exposure, 6.1 Visit schedule, 6.1.2.4 Week 16 (± 7 days) (Visit 4) and every subsequent 16 weeks (± 7 days) thereafter, 6.1.2.5 Start of open-label treatment visit (*new section*), 6.1.2.6 End-of-study treatment visit, 6.3.1 Primary efficacy variable, 6.3.3.8 Health-related quality of life, 6.5.2 Assessment of tumour-related biomarkers

11.3.1.9 Modification 9: Additional language added to perform survival sweep

Language was added to include additional survival sweeps shortly after the database cut-off date for the MFS analysis and prior to any subsequent analysis of OS to ensure that OS data is current.

Protocol sections affected: Synopsis, 6.1 Visit schedule, 6.1.4 Unscheduled visits

11.3.1.10 Modification 10: Modification of dosing language

The wording for the study drug dose to be administered was modified: 600 mg (2 tablets of 300 mg) twice daily with food, equivalent to a total daily dose of 1200 mg.

The change was done to align darolutamide dosing wording across the development program.

Protocol sections affected: Synopsis

11.3.1.11 Modification 11: Nomenclature change

With the approval of the INN darolutamide, the Orion drug nomenclature (ODM-201) was replaced with darolutamide throughout the protocol. In addition, the Orion codes for darolutamide diastereomers and metabolite were replaced with trivial names in the entire document.

Protocol sections affected: Abbreviations and definition of terms (*new subsection added*), the entire document (amended sections are not indicated in the protocol body)

11.3.1.12 Modification 12: Personnel change

The sponsor's medically responsible person was changed as a result of personnel change.

Protocol section affected: Signature of the sponsor's medically responsible person

11.3.1.13 Modification 13: Other clarifications and corrections

- The wording of exclusion criterion 15 was harmonised between synopsis and Section 4.3.
- PFS was removed from the list of follow-up assessments in the synopsis since PFS cannot be assessed/reported by site and unless a previous local/regional progression (not evaluated as metastasis) MFS and PFS would be coincidental.
- The wording was harmonised throughout the protocol to state that **approximately** 1500 patients will be randomised and **approximately** 600 patients will participate in the PK sampling.
- The guidance for ECG and vital signs measurements was further clarified in Table 3 and in Section 6.6.2.
- An error was corrected: a footnote referring to pain diary completion was removed from the PK diary collection row in Table 3.
- The definition of the pain progression was corrected in section 6.3.2.4 since the data will not be collected at screening (day 1 is considered baseline).
- Since the data related to clinical studies with darolutamide was not updated in the introduction section, it was clarified that more detailed information is available in the latest available version of the IB.
- The abbreviation for AUC_{0-X} was corrected in the list of abbreviations.
- The sentence related to local amendments was removed from the cover page since there are no local amendments for this study.

Protocol sections affected: Cover page of the integrated protocol, Synopsis, Abbreviations and definitions of terms, 1.5 Clinical studies with darolutamide, 4.1 Number of patients, 4.3 Exclusion criteria, 6.1 Visit schedule, 6.3.2.4 Time to pain progression, 6.6.2 Clinical safety assessments, 7.7.4 Evaluation of pharmacokinetics

11.3.2 Changes to the protocol text

Changes to the protocol text are provided in a separate track changes version.

11.4 Amendment 4

Amendment 4 is a global amendment dated 06 JUL 2019.

11.4.1 Overview of changes to the study

Section # and name	Description of change	Rationale

Synopsis 6.1 Visit schedule 6.1.2.6 End-of-study treatment visit 6.1.3 Follow-up period 6.1.5 Roll-over study (new section) 6.1.6 End of study (new section) 7.4 General statistical considerations
	
The option for patients currently receiving treatment in this study to continue treatment in a roll-over study was added. Statistical considerations were described. The end of the study was defined.
	
To enable patients who are receiving darolutamide treatment in the current study to continue to receive darolutamide treatment when the study is completed. The section for the end of the study was added for completeness and clarity.

5.7.3 Drug-drug interactions
	
The recommendation to avoid concomitant use of moderate CYP3A4 inducers was deleted (while strong CYP3A4 inducers should still be avoided).
	
Recent results have established the darolutamide exposure-response relationship which showed a flat relationship (maximum PSA response) over the entire exposure range of 600 mg BID and also at exposures below that range. Thus, even with a darolutamide exposure decrease of 50% (potentially driven by a CYP3A4 inducer), there would still be sufficient effect on PSA. Therefore the modification allows the use of moderate CYP3A4 inducers.

Synopsis 3 Overall study design and plan 4.7.1 Reasons for discontinuation of study 4.7.2 Reasons for withdrawal from study treatment 4.7.2.1 Confirmed metastasis
	
Open-label study wording was updated to:
 
 • describe the endpoint of the study visits and follow-up • describe the local and central reading requirements for metastasis assessments • add guidance related to discontinuation of study 	
Modifications were made for clarity for the open-label part of the study, and to correct an inconsistency related to ECG requirements.

Section # and name	Description of change	Rationale
6.1 Visit schedule 6.1.2.6 End-of-study treatment visit 6.1.3 Follow-up period 6.2 PK assessments during double-blind treatment	treatment • clarify the time points of ECG collection	
Title page Signature of the sponsor's medically responsible person	The sponsor's medical expert / medically responsible person was changed.	Administrative change
11.2.2 Changes to the protocol text	The old/new text detailed comparison from protocol amendment 2 was removed and a reference to amendment 2 was added.	For brevity, to improve readability, and to reduce complexity of the protocol.
5.7.2 Prohibited treatments	The sentence "Concomitant treatment with another systemic antineoplastic therapy (except GnRH) or another investigational medicinal product" was removed.	To reduce redundancy within the section.

11.4.2 Changes to the protocol text

Changes to the protocol text are provided in a separate track changes version.

12. APPENDICES

- [Appendix 1.](#) Investigator consent page
- [Appendix 2.](#) Routing and time frames of serious adverse event reporting
- [Appendix 3.](#) ECOG performance status
- [Appendix 4.](#) Brief Pain Inventory – Short Form
- [Appendix 5a.](#) FACT-P

- [Appendix 5b.](#) PCS subscale of FACT-P
- [Appendix 6.](#) EQ-5D-3L
- [Appendix 7.](#) EORTC-QLQ-PR25
- [Appendix 8.](#) List of strong and moderate CYP3A4 inducers

Appendix 2. ROUTING AND TIME FRAMES OF SERIOUS ADVERSE EVENT REPORTING

cd	calendar day	SAE	Serious Adverse Event
*	fatal and life-threatening event	SUSAR	Suspected Unexpected Serious Adverse Reaction
EC	Ethics Committee	EDC	Electronic Data Capture
IRB	Independent Review Board		

Appendix 3. ECOG performance status

Grade	ECOG performance status
0	Fully active, able to carry on all pre-disease performance without restriction
1	Restricted in physically strenuous activity but ambulatory and able to carry out work of a light or sedentary nature, e.g., light house work, office work
2	Ambulatory and capable of all self-care but unable to carry out any work activities. Up and about more than 50% of waking hours
3	Capable of only limited selfcare, confined to bed or chair more than 50% of waking hours
4	Completely disabled. Cannot carry on any selfcare. Totally confined to bed or chair
5	Dead

Appendix 4. Brief Pain Inventory – Short Form

CCI

A large black rectangular redaction box covers the majority of the page content below the section header. The text "CCI" is visible in the top-left corner of this redacted area.

CCI

Appendix 5a. FACT-P

CCI

CCI

CCI

Appendix 5b. PCS subscale of FACT-P

Appendix 6. EQ-5D

CCI

A large black rectangular redaction box covers the majority of the page content below the section header. The text "CCI" is visible in the top-left corner of this redacted area.

CCI

A large black rectangular redaction box covers the majority of the page content. The text "CCI" is visible in the top-left corner of this redacted area.

CCI

A large black rectangular redaction box covers the majority of the page content. The text "CCI" is visible in the top-left corner of this redacted area.

Appendix 7. EORTC-QLQ-PR25

CCI

A large black rectangular redaction box covers the majority of the page content below the section header. The text "CCI" is visible in the top-left corner of this redacted area.

CCI

A large black rectangular redaction box covers the majority of the page content, starting below the header and extending nearly to the bottom. The text "CCI" is visible in the top-left corner of this redacted area.

Appendix 8. List of strong and moderate CYP3A4 inducers

Strong

Ajmaline phenobarbital
Carbamazepine
Enzalutamide
Fosphenytoin
Hypericum perforatum (St. John's Wort)
Lumacaftor
Methylphenobarbital
Mitotane
Phenobarbital
Phenytoin
Primidone
Propranolol phenobarbital
Rifabutin
Rifampicin
Rifamycin
Rifapentin

Moderate

Bosentan
Efavirenz
Etravirine
Lopinavir
Mephenytoin
Modafinil
Nafcillin

## List of Abbreviations

AE	Adverse Event
BMI	Body Mass Index
CI	Confidence Interval
CRF	Case Report Form
ECG	Electrocardiogram
FAS	Full Analysis Set
HLGT	High level group term
HLT	High level term
MedDRA	Medical Dictionary for Regulatory Activities
MLG	MedDRA Labelling Grouping
n	Number of non-missing values
N/A	Not Applicable
NCI-CTCAE	National Cancer Institute Common Terminology Criteria for Adverse Events
nmCRPC	Non-metastatic castration-resistant prostate cancer
PT	Preferred Term
QTc	Corrected QT
SAE	Serious Adverse Event
SAF	Safety Analysis Set
SAP	Statistical Analysis Plan
SOC	System organ class
TEAE	Treatment-Emergent AE
TESAE	Treatment-Emergent SAE
WHO-DD	World Health Organization Drug Dictionary

## 1. Introduction

Study 17712 (ARAMIS) is a multinational, randomized, double-blind, placebo-controlled, phase III efficacy and safety study of darolutamide in men with high-risk non-metastatic castration-resistant prostate cancer (nmCRPC).

This supplement to the statistical analysis plan (SAP) describes the analyses and data presentations for final clinical study report addendum when all patients have discontinued the trial.

This SAP Supplemental 7 version 1.0 is based on integrated protocol version 5.0 (amendment 4) dated 06 JUL 2019, on Supplemental 4 SAP version 1.0 dated 04 DEC 2019 and SAP v4.2 dated 20 SEP 2018.

## 2. Study Objectives

Refer to main SAP v4.2 dated 20 SEP 2018.

### **3. Study Design**

Refer to main SAP v4.2 dated 20 SEP 2018.

### **4. General Statistical Considerations**

Refer to main SAP v4.2 dated 20 SEP 2018.

### **5. Analysis Sets**

Refer to main SAP v4.2 dated 20 SEP 2018.

### **6. Statistical Methodology**

The statistical analyses will be descriptive. Summaries will be provided for both treatment groups, darolutamide and placebo.

For disposition tables, concomitant medications, concurrent procedures, study-drug exposure tables and adverse events tables, the patients who switched from placebo to darolutamide during the open-label period will be displayed. These following treatment groups will be shown: darolutamide total (double-blind and open-label periods), darolutamide double-blind period, placebo double-blind period, placebo-darolutamide cross-over patients.

#### **6.1 Population characteristics**

##### **6.1.1 Disposition of patients**

A summary table will be presented for the number of patients enrolled and the number and percentage of patients in each of the defined populations. Re-screened patients will only be counted once.

The reasons for patients excluded from each of the patient populations will also be tabulated. The reasons for discontinuation of study treatment will be tabulated.

##### **6.1.2 Demographic and Baseline Characteristics**

No demographics and baseline characteristics analyses will be performed in this addendum.

### 6.1.3 Medical history

No medical history analysis will be performed.

### 6.1.4 Prior and concomitant medications

The following concomitant medications and procedures tables will be created:

- Concurrent diagnostic and therapeutic procedures: frequency of patients by procedure
- Concomitant medications: frequency of patients for each drug category
- Concurrent diagnostic and therapeutic procedures related to adverse event (AE): frequency of patients by procedure

The dictionary used for coding medications is the WHO Drug Dictionary.

Concomitant medications, subsequent treatment and concurrent procedures will be displayed for darolutamide total (double-blind and open-label periods), darolutamide double-blind period, placebo double-blind period, placebo-darolutamide cross-over patients.

If the start date of the concomitant medications or concurrent procedures is missing, the respective medications or procedures will be considered under the double-blind period.

In addition to the full analysis set (FAS) population, concomitant medication will also be summarized for the safety analysis set (SAF) population.

## 6.2 Efficacy

No efficacy analyses will be performed, only follow-up time will be presented.

The duration of follow-up, defined as time from randomization to last contact or death at the database cut-off date, will be summarised using descriptive statistics (number of observations, mean, standard deviation, minimum, median and maximum).

## 6.3 Pharmacokinetics/pharmacodynamics

No pharmacokinetic analyses will be performed.

## 6.4 Biomarker evaluation

No biomarker analyses will be performed.

## 6.5 Safety

All data including the open-label period will be summarized.

For patients randomized to darolutamide, safety events will be displayed separately for:

- the double-blind period

- the double-blind and open-label periods (total)

For patients randomized to placebo, safety events will be displayed separately for:

- the double-blind period
- the open-label period after cross-over to darolutamide treatment

The double-blind period of the study only will be considered for risk difference, risk ratio, interval-specific incidence and prevalence.

If the start date of the AE is missing then the event will be considered occurring during the double-blind period.

No formal statistical tests will be done for the safety endpoints. All analyses for safety will be performed in the SAF population.

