Collection of AEs and SAEs considered to be related to study treatment or procedures	X	X	X ⁵	X ⁵
Collection of concomitant treatments used to treat new related or unresolved related AEs	X	X	X	X
Darolutamide dispensing and accountability			X	X ⁷
First SSE	X	X	X	X
First prostate cancer-related invasive procedure for prostate cancer	X	X	X	X
Survival status ⁸	X	X	X	X
Serum PSA	X		X ⁶	
Chest, abdomen, and pelvic CT/MRI	X		X ⁶	
Bone scan ⁴	X		X ⁶	

Abbreviations: ECOG = Eastern Cooperative Oncology Group; EOS = end-of-study; PSA = prostate-specific antigen; SSE = symptomatic skeletal event

* Note: In case a patient initiates a prohibited treatment during the open-label treatment phase before metastasis confirmed by local reading, the patient must discontinue study treatment and will be followed for survival until the end of the study (see Section 4.7.1 for additional details).

¹ Until metastasis, death, transition to a roll-over study, or the end of the study

² Until death or the end of the study

³ Patients will be instructed to complete the diary for 6 days before each 16-week visit until documented pain progression. Pain medications will be recorded on CRFs at each 16-week visit until documented pain progression.

⁴ New lesion(s) in bone scan must be confirmed by CT/MRI (whichever imaging was conducted at screening for soft tissue) or x-ray. If confirmatory scan is negative (does not confirm progression), the patient will continue to visit study centre as specified in the study event table.

- ⁵ For placebo patients crossing over to open-label darolutamide, all AEs and SAEs irrespective of relatedness will be captured.
- ⁶ Placebo patients crossing over to open-label darolutamide will have central PSA testing and local imaging, radiology .
- ⁷ Only drug accountability performed at the end-of-study treatment visit.
- ⁸ Survival data will also be collected through an additional survival sweep. All patients considered alive shortly after the database cut-off date for the MFS analysis and prior to any subsequent analysis of OS will be contacted for survival status.

Patients initiating a prohibited treatment before confirmed metastasis will be followed only for survival status every 16 weeks until the end of the study.

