8.8.5 Database lock

When all data for the double-blind period of the study have been entered and all queries resolved the data will be locked. Entire database will be locked after all data for the follow-up period of the study have been entered and queries resolved. Only authorised and well-documented updates to the study data are possible after the database locks. The locked data will be used in the statistical analyses for study reporting.

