8.8.6 Opening of the treatment code

The treatment code will be opened after the double-blind data are locked. The treatment codes will be available in the EDC after code opening.

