### **6.5.2 Adverse events**

All adverse events (AE) whether considered drug-related or not, will be reported on the case report form (CRF) with diagnosis, start/stop dates, dates of any grade change, action taken, whether treatment was discontinued, any corrective measures taken, and outcome. For all events, the relationship to treatment and the severity of the event will be determined by the Investigator. AEs will be classified and coded using the National Cancer Institute (NCI) Common Terminology Criteria Adverse Event (CTCAE), version 4.03.

The treatment period for this study, for purposes of safety analyses, extends from the initiation of study treatment until 30 days after the last administration of study treatment.

Each change in AE grade was entered as a separate record with no automatic link to the original AE record, which may lead to variations of the verbatim for the same AE. This makes a correct grouping of AE grades, which actually belong together, not always possible. An AE is considered as treatment-emergent (TEAE) if there is an AE record which starts during treatment or within the post-treatment time window of 30 days.

For further definitions of the terms AE, SAE, seriousness, intensity, causal relationship with treatment, causal relationship to protocol-required procedures, action taken, and outcome; see Protocol Section 6.6.1.

Descriptive summary tables (frequency and percentage of patients, not of events) will be presented by treatment group and MedDRA version 24.0, or the most recent version for the following:

- Pre-treatment AEs
- TEAEs
- TEAEs with grade 3, 4, or 5
- TEAEs occurring in at least 1% of patients
- TEAEs occurring in at least 5% of patients
- TEAEs leading to study drug withdrawal
- TEAEs leading to dose reduction
- TEAEs leading to drug interruption
- TEAEs leading to dose reduction and/or drug interruption
- Drug-related TEAEs
- Drug-related TEAEs with grades 3, 4, or 5
- Drug-related TEAEs occurring in at least 5% of patients in any treatment group
- Drug-related TEAEs leading to study drug withdrawal
- Drug-related TEAEs leading to dose reduction
- Drug-related TEAEs leading to drug interruption
- Drug-related TEAEs leading to dose reduction and/or drug interruption
- Interval specific and cumulative event rates for TEAEs (for TEAEs with at least a 5% total incidence rate (any grade)).
- Post-treatment non-treatment-emergent AEs

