#### **Safety variables, Medical history, and Concomitant medications:**

Treatment emergent AEs, treatment phases, period and relative days will be derived according to data management programming, the operational manual document and standard guidelines.

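### Supplement 7 places every AE with no start date in the double-blind period, so an undated AE arising on open-label darolutamide in a crossover man could be shown under placebo

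*SAP*

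**What the plan says.** Supplement 7 covers the final report addendum, after all patients have left the trial. Section 6 says that for disposition, exposure, medication, procedure and AE tables "the patients who switched from placebo to darolutamide during the open-label period will be displayed". It then lists four groups: darolutamide total, darolutamide double-blind, placebo double-blind, and placebo-to-darolutamide crossover. Section 6.5 repeats the split for safety events and limits the comparative measures to the double-blind period.

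The rule for undated events is in the same section: "If the start date of the AE is missing then the event will be considered occurring during the double-blind period". Section 6.1.4 gives medications and procedures the same default: "the respective medications or procedures will be considered under the double-blind period".

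Two other texts bear on this. Table 4 of the protocol (section 6.1, footnote 5) provides that "For placebo patients crossing over to open-label darolutamide, all AEs and SAEs irrespective of relatedness will be captured". Section 6.5.2 of Supplement 7 says AEs "will be reported on the case report form (CRF) with diagnosis, start/stop dates", along with the dates of any grade change.

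**The concern.** With only one treatment, putting an undated event in the treatment period is a cautious default. A crossover man has two treatment periods on different treatments, and this default always chooses placebo. It can take an event out of the crossover column but can never put one in. That column is where Supplement 7 displays safety after the switch to darolutamide.

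The rule also ignores information that could settle some cases: the stop date, the dates of grade changes, the visit at which the AE was reported (if stored), and whether the AE was already in the data locked before unblinding.

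What is at stake is the accuracy of a descriptive display. It matters most for rare special-topic events such as seizure, where one patient is visible.

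**Working it through.** The plan states no figure on this point, so there is nothing to reproduce. The check traces one event through the rules and then sizes one misplaced patient.

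**Trace.** Take a placebo-randomised man who crosses over and has an AE on open-label darolutamide whose record has no start date.
1. The AE is captured whether or not it is judged related (protocol Table 4, footnote 5).
2. Supplement 7 section 6.5 assigns it to the double-blind period.
3. His double-blind events belong in the placebo double-blind column and his later events in the crossover column, so this AE goes to placebo and is absent from crossover.
4. This affects TEAE tables only if the record counts as treatment-emergent. Section 6.5.2 defines a TEAE by when the record starts and is silent on a record with no start.
5. If it counts, it can enter the double-blind risk difference and risk ratio. It can also enter the double-blind rate per 100 patient-years in section 6.5.2, which divides the number of events by treatment time. There it adds to the placebo numerator an event that did not arise in placebo exposure. The exposure-adjusted table for fracture, weight decrease, cardiac disorders and fall has no crossover column at all.

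**Inputs for size.** Planned arms are 1000 darolutamide and 500 placebo (main SAP v4.2, section 3.1). The documents give neither the number of crossovers nor the number of undated AEs. I assume 50 to 250 crossovers, and all event counts below are also assumed.

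**Incidence columns.** One patient with no other qualifying event in the row changes a column by 100/n percentage points.
- Crossover: 100/50 = 2.0; 100/150 = 0.67; 100/250 = 0.4. For example, 3/150 (2.0%) becomes 2/150 (1.3%).
- Placebo double-blind: 100/500 = 0.2.

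**Double-blind risk ratio.** RR = (a/1000)/(b/500), with SE(log RR) = √(1/a − 1/1000 + 1/b − 1/500). The same rule also moves undated open-label AEs of darolutamide-randomised men into their double-blind column, so both arms are shown.

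| Misplaced patients | Rare event: a v b | RR (95% CI) | Common event: a v b | RR |
|---|---|---|---|---|
| none | 10 v 5 | 1.00 (0.34 to 2.91) | 120 v 60 | 1.00 |
| 1 placebo | 10 v 6 | 0.83 (0.30 to 2.28) | 120 v 61 | 0.98 |
| 1 darolutamide | 11 v 5 | 1.10 (0.38 to 3.15) | 121 v 60 | 1.01 |
| 1 placebo, 2 darolutamide | 12 v 6 | 1.00 (0.38 to 2.65) | 122 v 61 | 1.00 |
| 1 placebo, 3 darolutamide | 13 v 6 | 1.08 (0.41 to 2.83) | 123 v 61 | 1.01 |

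The ratio can move either way or not at all. Every point estimate stays well inside its starting interval, which for the common event is 0.75 to 1.34.

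**The case against.** **There may be no such AE.** Start dates are on the CRF, edit checks look for missing data (protocol 8.8.3), and queries are resolved before each lock. No document shows an undated AE. This stands, and the point must remain conditional.

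**An undated record may not be a TEAE.** This also stands. If such records are excluded, the placebo TEAE column and the risk ratio are untouched.

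**Other text may govern.** Main SAP section 5, adopted by Supplement 7, analyses under placebo only men who never received darolutamide. But Supplement 7 sets its own columns by randomised arm and period, so this does not move the event to the crossover column. Main SAP section 4.3 says "Treatment emergent AEs, treatment phases, period and relative days will be derived according to data management programming" and refers to further documents not available here. The sentence in section 6.5 may be a last resort after those steps, but nothing in the text says so. Protocol 7.4 imputes incomplete event dates to the earliest possible date. That is an analogy for wholly missing dates, not a rule about which treatment column an event belongs in.

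**Any other default also misclassifies.** This is the strongest objection. A stop date after the first open-label dose does not show that the AE began on open-label drug. Extending a new default to darolutamide-randomised men could remove true double-blind events from the randomised comparison. For medications, an unknown start may simply mean long-standing use. These objections limit the remedy to crossover men and AEs. They do not justify a rule that ignores the other recorded dates.

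**Conclusion.** The point holds in conditional form and is minor. As written, the rule would misplace an undated AE that arose on open-label darolutamide in a crossover man, provided the AE is counted at all. On the assumed crossover numbers, each such patient takes 0.4 to 2.0 percentage points off a crossover incidence and adds 0.2 to placebo. If there are no undated AEs, the effect is nil.

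A reader might infer that the rule tilts the double-blind comparison towards darolutamide. The documents do not support that: the rule acts in both arms, misplacement in the 2:1 allocation ratio leaves the ratio at 1.00 in the example, and no counts are given. A reader might also infer that events have in fact been misplaced, but nothing shows this.

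The outputs are descriptive with no formal safety tests, and the main SAP's safety analysis at the MFS cut-off does not use this rule. No conclusion of the trial is threatened.

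**What to change.** Add to section 6.5 of Supplement 7, for placebo-to-darolutamide crossover men only:

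*An AE with a missing start date is assigned to the double-blind period if it is already in the locked double-blind data, or if its stop date, a grade-change date or its recorded visit precedes the first open-label dose; otherwise it is assigned to the open-label crossover column. The number of AEs with a missing start date is reported by column, for all columns.*

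The locked-data condition rests on the protocol's sequence. Section 8.8.5: "When all data for the double-blind period of the study have been entered and all queries resolved the data will be locked". Section 8.8.6: "The treatment code will be opened after the double-blind data are locked". An AE already in that lock was therefore reported before unblinding and cannot have arisen on open-label drug.

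Keep the present default for all other patients, and leave section 6.1.4 as it is for medications and procedures.

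The cost is a short text change and a count. Stop and grade-change dates are already on the CRF. The documents do not confirm that a visit is stored with each AE; if it is not, that condition simply does not apply. The downside is that some double-blind events may be shown as crossover darolutamide events. That slightly overstates the crossover column, which is the cautious direction for a safety display. If the reported count is zero, the question is closed.
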